2. OBJECTIVES & OUTCOMES

1. Objectives

The main objective is to assess the performance of selected RMTs against ADL standard clinical questionnaires in finding differences among individuals of various classes of severity of AD and investigate if RMT measurements are more precise and better reflect disease progression and functional /QoL changes compared to ADL standard measurements.

Secondary objectives:

- to assess associations between RMT measurements and standard clinical scales used to assess specific clinical conditions and functional impairments in AD patients;
- to assess if RMT measurements are more precise and more ecological;
- to investigate the patient acceptability and user-friendliness of selected RMTs;
- to assess the technical performance of RMTs in a real-life setting.
- to assess associations between RMT measurements, standard clinical scales and AD-related biomarker in blood and CSF
- to explore new AD-related biomarkers.

To achieve the non-invasive aspect of these objectives, measurements will be performed in clinic (i.e. under supervision of a clinical team) and in non-clinical, real life settings (i.e. at home, at work, etc.).

Primary Outcome

- Difference between healthy controls, subjects with preclinical AD, subjects with MCI due to AD, and subjects with mild-to-moderate AD dementia using selected RMTs measurements aimed to profile ADL, using diagnostic criteria as defined under 3.1.3" Both primary and secondary outcomes.

¹ Buegler, M, Harms, RL, Balasa, M, et al. Digital biomarker-based individualized prognosis for people at risk of dementia. *Alzheimer's Dement*. 2020; 12:e12073. <https://doi.org/10.1002/dad2.12073>

Evaluation of a Computerized Complex Instrumental Activities of Daily Living Marker (NMI) (AltoidaML)

Secondary Outcomes

- Established clinical measures: difference between healthy volunteers, subjects with preclinical AD, subjects with MCI due to AD, and subjects with mild-to-moderate AD dementia in the following assessments of specific functions when performed in the clinic (in brackets, it is indicated which functional domain and/or main outcome measure is covered by the assessment):
 - Amsterdam-iADL
 - (orientation, planning skills & memory required for task completion household management).
 - ADCS-ADL
 - (orientation, planning skills & memory required for task completion household management).
 - CERAD neuropsychological test battery
 - (orientation, planning skills, memory required for task completion, word-finding difficulties).
 - Geriatric Depression Scale
 - (low mood, anhedonia, withdrawal).
 - Neuro Psychiatric Inventory
 - (agitation, psychoses, apathy)
 - Body Mass Index (BMI)
 - Presence diabetes or pre-diabetes diagnosis
 - Exercise, [measured with Godin Leisure-time exercise questionnaire]
 - metabolic profile (plasma cholesterol, glycaemia, HbA1S). Only if information is available a priori.
 - APOE-e4 allele genotype as obligatory measurement.
 - smoking [asked at the clinic and reported as number of cigarettes per day]
 - drinking habits [asked at the clinic and reported as units of alcohol/ week]
 - diet supplement [asked at the clinic and reported as the number of supplements currently taken]
 - hobbies [asked at the clinic using validated tools for measuring cognitive reserve and/or reported as number of activities/week (i.e., reading, crossword, puzzle solving, listening or playing music, painting, gardening, backing) the time (hour/week).

Evaluation of a Computerized Complex Instrumental Activities of Daily Living Marker (NMI) (AltoidaML)

- RMT assessments: difference between healthy volunteers, subjects with preclinical AD, subjects with MCI due to AD, and subjects with mild-to-moderate AD dementia in the following assessments performed in the real world (non-clinical settings):
 - Altoida NMI telehealth version (tablet, smartphone, active interface)
 - Orientation, planning skills & spatial memory required for task completion.
 - Executive function skills & prospective memory required for task completion, short and long term.
 - Mood & anxiety
 - Voice & speech analysis
 - Accelerometer, dominant hand - arm movement,
 - Gait and motility at home etc.
- Evidence of RMT ecological value, using QoL changes, by statistical association (e.g., correlation, regression) between measurements collected in clinic vs. measurements collected in real life within the same functional domain(s).
- Quantification of passively collected sensor signals during specific ADL performance captured within context-defined, time-tagged epochs (beginning and end) repeatedly occurring over the trial period provided by:
 - the subject
 - the caregiver/informant
 - the portable camera (when available).

Evaluation of a Computerized Complex Instrumental Activities of Daily Living Marker (NMI) (AltoidaML)

Table 2: list of assessments classified by test setting (clinic or real life) and completers.

| Setting | Completed by | Test/device name | Frequency | Time (minutes) | Functional domain(s) and/or test domain(s) covered |
|---------|--------------|---|-----------|----------------|--|
| Clinic | Patient | Demographics, medical history, medication use | Once | 10 | Life habits & AD risk factors |
| | | Physical examination | Once | 10 | Life habits & AD risk factors |
| | | Godin Leisure-time exercise questionnaire | Once | 5 | Life habits & AD risk factors |
| | | CERAD test battery | Once | 20 | |
| | | • Verbal fluency (animal naming) | Once | 5 | Word finding difficulties |
| | | • 15 item Boston Naming Test | Once | 5 | Planning skills & memory, Word finding difficulties |
| | | • Mini Mental State Examination | Once | 5 | Orientation, Planning skills & memory, Word finding difficulties |
| | | • Word list learning | Once | 5 | Word finding difficulties |
| | | • Word list recall | Once | 5 | Planning skills & memory, Word finding difficulties |
| | | • Word list recognition | Once | 5 | Planning skills & memory, Word finding difficulties |
| | | • Constructional praxis | Once | 5 | Planning skills & memory |
| | | • Delayed constructional praxis | Once | 5 | Planning skills & memory |
| | | Digit Symbol Substitution Test | Once | 5 | Planning skills & memory |
| | | Altoida Medical Device | Once | 20 | Orientation, Planning skills & memory |
| | | Physical functioning tests | Annual | 10 | Gait |
| | | • 1-minute walking test | Once | 5 | |
| | | • 1-minute dual walking test | Once | 5 | |
| | | • Timed up-and-go test | Once | 5 | |
| | | Social Functional Scale | Annual | 5 | Maintaining social roles |
| | | Geriatric Depression Scale | Annual | 5 | Motivation |
| | | Body Mass Index (BMI) | Annual | 5 | Life habits & AD risk factors |
| | | Clinical Dementia Rating | Annual | 20 | Orientation, Household management, Use of technology, Maintaining social roles |
| | | ADCS-ADL | Annual | 20 | Orientation, Planning skills & memory, Household management |
| | | Diabetes or pre-diabetes | Annual | 5 | Life habits & AD risk factors |
| | | Clinical Dementia Rating | Annual | 20 | Orientation, Household management, Use of technology, Maintaining social roles |

Evaluation of a Computerized Complex Instrumental Activities of Daily Living Marker (NMI) (AltoidaML)

| | | | | | |
|--|--|---------|------|---|-------------------------------|
| | | Smoking | Once | 5 | Life habits & AD risk factors |
|--|--|---------|------|---|-------------------------------|

Evaluation of a Computerized Complex Instrumental Activities of Daily Living Marker (NMI) (AltoidaML)

2. Study design

The study is a multicentre, observational, cross-sectional, digital assessment cohort study in subjects with preclinical AD, MCI due to AD, and mild-to-moderate AD dementia. It consists of two parts: the main study (tier 1), where the subjects are provided with wearable digital devices, and a sub-study (tier 2), in which technologies are installed in the subjects' home (see table 2 above). The duration of the main study for individual subjects is 5 years of data collection, while for the sub-study (tier 2) a similar period of data collection is expected, with a flexible time between the two studies for arranging home-device wiring. The sub-study will be performed on those volunteers whose home setting shows the necessary technical requirements (please see table 2 above for the Residential Movement Detector).

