Objectives: The primary objective of this study is to assess the performance of selected RMTs against standardised rating scales of ADLs in subjects with preclinical AD dementia, MCI due to AD dementia, and mild-to-moderate AD dementia. Secondary objectives are, (a) to evaluate associations between RMTs and standard clinical scales used to characterise people with AD diagnosis, (b) to investigate the patient acceptability of selected RMTs used for the duration of the study, and (c) to assess the technical performance of RMTs and digital platform in a real-life setting.

Study design: A multicentre observational cross-sectional cohort digital assessment study lasting 5 years, with a sub-study extension of at-home monitoring for 4 weeks.

Study population: Subjects (n=283) with positive AD biomarkers, e.g positive brain Abeta (A β) deposition confirmed by amyloid PET or CSF A β test at the preclinical AD, MCI due to AD, and mild-to-moderate AD dementia stages, and age-and gender matched control subjects (n=213) aged over 50 years with a caregiver/family member available to contribute to the study.

Primary outcome measure: statistically significant difference between healthy volunteers, preclinical AD, MCI due to AD, and mild-to-moderate AD dementia in outcome measures of ADL using selected RMTs.

1. **Secondary Outcome measurements:** Statistically significant difference between healthy volunteers, preclinical AD, MCI due to AD, and mild-to-moderate AD dementia using RMTs, neuropsychological assessment like CDR and Altoida's cognitive scale. Finally the relationship of genes or biomarkers with risk of RMT progression, and longitudinal correlation changes in biomarkers with rate of RMT progression.

Evaluation of a Computerized Complex Instrumental Activities of Daily Living Marker (NMI) (AltoidaML)

2. Assess effectiveness of disease modifying therapy such as aducanumab in real world clinical practice on subjects who will initiate disease modifying therapy for AD treatment during the study by using neuropsychological assessment such as CDR and fluid biomarker including blood and CSF and so on.
3. Assess effectiveness of disease modifying therapy such as aducanumab in real world clinical practice on subjects who will initiate disease modifying therapy for AD treatment during the study by using RMTs and Altoida's cognitive scale.

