The central assumption of the study is that functional disabilities proportionally increase with the progressive worsening of the disorder. A recent classification proposed by the FDA 2018 guidelines for the development of novel treatments in Preclinical AD identifies the early disease progression in 3 stages: (a) Patients with characteristic pathophysiologic changes of Preclinical AD but no evidence of clinical impact (Stage 1) (b) Patients with characteristic pathophysiologic changes of AD and subtle or more apparent detectable abnormalities on sensitive neuropsychological measures, but no functional impairment (Stage 2), and (c) Patients with characteristic pathophysiologic changes of AD and subtle or more apparent detectable abnormalities on sensitive neuropsychological measures, but mild and detectable functional impairment. (Stage 3). The aim of the RADAR-AD study is to assess the feasibility, utility and performance of selected RMTs in profiling ADL in real-world settings [2, 3]. This goal will be achieved by evaluating digital signals collected either continuously, or daily, or weekly at home, either using wearable devices or home-located ambient devices, determining as much as possible the specific context-dependent conditions in which the signals are measured. As a general hypothesis, we expect that RMTs will deliver more sensitive and less variable measurements when compared to standard clinical assessments, questionnaires and tests measuring specific functional capabilities in the clinics.

The most important results of the present study will be (1) the evidence that some RMT parameters will provide insights for lower variance than the standard scales or

Evaluation of a Computerized Complex Instrumental Activities of Daily Living Marker (NMI) (AltoidaML)

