6. STATISTICAL ANALYSIS

Data obtained from RMTs will be either continuous (as, for example, accelerometer recording having several samples per second, participant's relative locations recorded via GPS every 5 minutes, ...) or obtained during a single clinical visit only (as, for example, gait assessment). Continuous raw data will be analytically processed and features characterizing behaviour per day will be obtained. For example, actigraphy read-outs will be used to derive sleep characteristics using Cole-Kripke algorithm (duration, quality of sleep, etc.) for every night, relative location data will be used to estimate distance travelled per day, duration of home stay per day, number of places visit per day and so on. Complete strategy for handling multi-sensor data and list of relevant features will be developed through the project duration. At the end, RMT data will be either a day-by-day time series or obtained at a single study time point.

We will analyse each RMT measurement separately, characterizing their variance to assess, whether 1) they are different between following groups: (a) healthy volunteers and (b) subjects with preclinical AD, (c) subjects with MCI due to AD, and (d) subjects with mild-to-moderate AD dementia, and 2) whether they are related to standard clinical questionnaires for ADL. For a continuous day-by-day time series, we will model such a RMT measure using a mixed-effect model for repeated measures (MMRM) based on observed case data. The model will include study group (or a related ADL scale), age, sex, and other related covariates/factors. Strength of between study groups difference (or relation to related ADL scale) is of primary interest. The within-participant covariance between visits will be estimated via an unstructured variance-covariance matrix. In case of convergence problems, alternative variance-covariance structures will be tried in the following order, with the first structure that converges being used in the analysis: heterogeneous Toeplitz, standard Toeplitz, and AR(1) with separate participant random effect. Weekdays and weekends time

Evaluation of a Computerized Complex Instrumental Activities of Daily Living Marker (NMI) (AltoidaML)

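### The main objective compares RMTs with ADL questionnaires, but as planned no analysis estimates the difference between the two

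*Combined protocol and SAP*

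**What the plan says.** Section 2 (Objectives & Outcomes) sets a main objective in two parts. The first is to "assess the performance of selected RMTs against ADL standard clinical questionnaires in finding differences among individuals" in different AD severity classes. The second is to "investigate if RMT measurements are more precise and better reflect disease progression and functional /QoL changes compared to ADL standard measurements". The Summary states the primary objective in the same direction, to "assess the performance of selected RMTs against standardised rating scales of ADLs", and section 1 adds that "we expect that RMTs will deliver more sensitive and less variable measurements when compared to standard clinical assessments".

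The outcomes are not comparative. The primary outcome is a difference between the four groups "using selected RMTs measurements aimed to profile ADL". Group differences on Amsterdam IADL and ADCS-ADL are listed separately, as secondary outcomes.

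Section 6 (Statistical Analysis) begins "We will analyse each RMT measurement separately". It models each RMT on study group, or alternatively on a related ADL scale. It then builds multivariate models that predict study group or an ADL scale, applies Bland-Altman analysis to tests done both in clinic and at home, and compares the predictive performance of home and clinical assessments.

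**The concern.** A claim that one instrument is more precise than another, or reflects disease better, is a claim about a difference between instruments measured in the same people. That difference needs its own estimate and interval.

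Association does not supply it, because an RMT that correlates well with a questionnaire can still separate the stages less well. Two sets of group tests read side by side do not supply it either, because one result can be significant and the other not when the true separations are equal. If section 6 is followed exactly, the report will contain results for RMTs and results for questionnaires but nothing that answers the main objective, and no stated standard for judging one better or more precise.

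**Working it through.** **1. Search of section 6 for an RMT-versus-questionnaire contrast**

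| Planned analysis | Role of the ADL questionnaire | Contrast estimated |
|---|---|---|
| MMRM or ANCOVA, one RMT at a time | Alternative explanatory variable to study group | Group effect on the RMT, or its relation to the scale |
| Multivariate models with cross-validation | Alternative prediction target | Predictive performance of RMT features |
| Bland-Altman | None | Clinic versus home version of the same test |
| Home versus clinical models | None named | Setting of assessment |

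No row gives a difference in effect size, AUC, standardised variability or sensitivity to progression between an RMT and a questionnaire. Section 6 does speak of characterising variance, but only that of the RMTs. Variances in different units cannot be compared without a common scale, and none is defined.

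**2. What the sample size implies for one contrast**

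The sample size section gives 55 per group for 80% power that all three adjacent-stage Welch t-tests on Amsterdam IADL are significant after Holm adjustment. The 55 cannot be reproduced, because the means and SDs come from a figure in a cited paper and are not in the documents. Simulating the stated rule, assuming equal steps and SD 1, gives joint power at n = 55 of about 64% for a step of 0.60 SD, 77% for 0.65 and 86% for 0.70. The implied step is therefore about 0.66 SD. At 0.65 SD a single two-sided 5% comparison has 92.6% power, about 93%.

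**3. Side-by-side tests when the two instruments are equally good**

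Let each instrument have power p for the same contrast. Each z-statistic then has mean 1.96 + a, where a is the standard normal quantile of p, and the two have correlation r. The chance that the RMT is significant and the questionnaire is not is

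P = (1 - p) - Φ₂(-a, -a; r),

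where Φ₂ is the bivariate normal distribution function. At r = 0 this is p(1 - p): 0.926 × 0.074 = 0.069, 0.80 × 0.20 = 0.16 and 0.50 × 0.50 = 0.25.

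| Power of each (assumed) | r = 0 | r = 0.3 | r = 0.5 |
|---|---|---|---|
| about 93% | 7% | 6% | 5% |
| 80% | 16% | 13% | 11% |
| 50% | 25% | 20% | 17% |

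These figures are per RMT and per contrast. The documents give no power for any RMT and no correlation between instruments.

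**4. Precision that a paired comparison would have**

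For standardised differences d₁ and d₂ in the same subjects, n per group and within-group correlation ρ,

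SE² = (2/n) × 2(1 - ρ) + (d₁² + d₂² - 2ρ²d₁d₂)/(4n).

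Take n = 55 and d₁ = d₂ = 0.65 (assumed):

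- ρ = 0.3: SE² = 0.0509 + 0.0035 = 0.0544, SE = 0.233. The advantage detectable with 80% power is 2.80 × 0.233 = 0.65 SD.
- ρ = 0.7: SE² = 0.0218 + 0.0020 = 0.0238, SE = 0.154. The detectable advantage is 2.80 × 0.154 = 0.43 SD.

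Power for a true advantage of 0.2 SD is about 13% to 25% over that range of ρ. With about 94 per group (283/3, assuming the AD subjects split equally) the detectable advantage is about 0.50 to 0.33 SD.

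**The case against.** **The study could still answer the question.** A reader might infer that it cannot. That goes too far. Group differences on RMTs and on both questionnaires are planned in the same four groups, so the material for a paired comparison will exist. What is missing is the planned comparison.

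**No p-value rule is stated.** A reader might also infer that superiority would be declared whenever one test is significant and the other is not. The documents contain no such rule, and section 6 puts the strength of the group difference first. The percentages above show why side-by-side tests are a poor substitute; they do not describe a decision rule in the plan. They also depend heavily on power: at the roughly 93% that n = 55 implies, they fall to 5-7%.

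**Home versus clinical models may cover it.** This is the best counter-argument. Section 2 describes the questionnaires as performed in the clinic and the RMT assessments as performed in the real world, so a clinical model could be read to include the questionnaires. But the sentence follows the text on tests done in clinic and repeated at home, with the Altoida app as example, and it reuses models built from RMT features. The natural reading is a contrast of settings, and even the broad reading names no questionnaire and no measure of the difference.

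**The objective may mean validation.** For stage separation the text says performance against questionnaires; the word better is attached to progression and functional or QoL change. Association would then answer part of the objective. But association with clinical scales is already a separate secondary objective, and the precision and progression clause is plainly comparative.

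**The feature list is still to be developed, and the study is observational.** Both are true. Neither prevents naming the comparator and the estimand now.

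**Conclusion.** The point stands in this form: as planned, the analysis does not answer the comparative main objective, because no analysis estimates the difference between an RMT and an ADL questionnaire. This follows from reading sections 2 and 6 together and depends on no calculation.

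The size is illustrative. With equal true separation, the RMT alone would be significant in about 5-7%, 11-16% or 17-25% of studies at 93%, 80% or 50% power each, for test correlations of 0.5 to 0. The 93% assumes equal steps and equal SDs, and also that an RMT would match the questionnaire's power. The paired precision figures rest on assumed standardised differences and correlations. The gap concerns the main question and should be closed before analysis.

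**What to change.** 1. Name Amsterdam IADL as the comparator questionnaire. Reconcile this with the sample size section, which counts its web version among the RMTs.
2. In the same subjects at baseline, for each adjacent-stage contrast, report the paired difference in AUC or standardised mean difference between each prespecified RMT and Amsterdam IADL, with a DeLong or bootstrap 95% confidence interval. For RMTs recorded at home, state which collection window is paired with the baseline questionnaire.
3. Add ADCS-ADL only where both groups receive the same version. Section 4.4.2 and the assessment descriptions give one version to preclinical and prodromal subjects and another to mild and moderate dementia, so MCI versus dementia has no common score as written. The version for controls is not stated.
4. In the multivariate step, compare cross-validated performance of the scale alone, RMTs alone, and both.
5. Base any claim of better or more precise on these differences, with multiplicity control across RMTs. Section 6 at present says only that correction will be considered.
6. Stage separation at baseline does not show progression. Limit progression claims to scales that are repeated: Table 2 lists ADCS-ADL as annual, while section 4.4.3 makes the end-of-study Amsterdam IADL optional.

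The cost is analysis-plan wording and some further analysis, with no new baseline data. The downside is that intervals may be wide, since the sample size was not derived for this comparison; the report should show them and not read an inconclusive difference as equivalence.
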